5.2 Primary Efficacy Endpoint

- Percent of successfully inserted SteadiSet IIS (i.e., those not withdrawn within 8 hours of
- insertion) that are not withdrawn from use prior to 7 days (168 hours) due to any of the
- 45 following:

42

48 49

50

51

52

53

54

62

63

64

65 66

67

68

69

70

71

- Blood glucose value ≥250 mg/dL with ketones >1.0 mmol/L, in the absence of illness or other physiological stress.
 - 2. Blood glucose value ≥250 mg/dL for at least 60 minutes duration, 3 hours or more following a snack or meal event AND failure to respond to up to 2 adequate corrective boluses delivered by the pump with a fall of at least 50 mg/dL. In the absence of BGM testing immediately prior to or following a corrective bolus then CGM values will be used for the primary endpoint analyses.
 - 3. Investigator advises the infusion set should be replaced to assure participant's safety.

5.3 Key Secondary Endpoint

- Proportion (%) of SteadiSet infusion sets withdrawn from use at any time following insertion
- prior to 7 days (168 hours) as evidenced by one or more of the following device failure modes.
- NOTE: infusion set removals prior to 168 hours due to miscalculation of date and/or time, along
- with other removals that cannot be ascribed to the investigational device performance, are
- 59 excluded from this proportion calculation.
- 1. Infusion set failure as defined in the Primary Endpoint (including any such removals occurring during the first 8 hours following set insertion)
 - 2. Evidence of infusion set site infection defined as requiring treatment or at the investigator's judgment
 - 3. Cannula dislodgement from subcutaneous (SC) space (with or without liquid leakage at the cannula insertion site)
 - a. Leakage at the cannula insertion site may or may not be deemed by the investigator to constitute infusion set failure following consultation with the study subject
 - b. Accidental removal events (e.g., tubing caught on doorknob) are excluded from this proportion calculation
 - 4. Occurrence of a non-resolvable pump occlusion alarm,
- 5. Other device malfunction (e.g., inability to pierce skin, bending, or other malformation that might impact insulin infusion, securement failure)

- 6. Presence of pain of sufficient severity to prompt early removal of infusion set
- 75 7. Any other event that can be ascribed to the investigational device performance that results in failure of insulin delivery

77 5.4 Safety Endpoints

- 78 Safety endpoints will comprise the incidence, severity, and relationship to the investigational
- device of all reported adverse events (serious and non-serious including DKA and severe
- 80 hypoglycemia) from the day of enrollment through the day of the final study visit or the day of
- 81 the first insertion + 98 days—whichever is earlier.
- Number of adverse events

83

89

90

91

92

93

94

95

96

98

99

100

103

104105

106

107

108

111

- Number of adverse device effects
- Number of serious adverse events
- Number of serious adverse events that are unanticipated adverse device effects
- Number of reportable hypoglycemic events as defined in the protocol
- Number of severe hypoglycemia events as defined in the protocol
- Severe hypoglycemia event rate per 100 person-years
 - Number of reportable hyperglycemic events with or without ketosis, as defined in the protocol
 - Number of diabetic ketoacidosis events as defined in the protocol
 - Diabetic ketoacidosis event rate per 100 person-years

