282	 Improved Continuous Subcutaneous Insulin Infusion (CSII) and insulin pump therapy options
283	 Reduced environmental waste
284	1.5.3 Risk Assessment
285 286 287	It is the assessment of the investigators that this protocol falls under DHHS 45 CFR 46.406 and 21 CFR 50.53 as a clinical investigation involving greater than minimal risk and no prospect of direct benefit to individual subjects, but likely to yield generalizable knowledge about the subjects' disorder or condition.
288	1.6 General Considerations
289 290 291	The study is being conducted in compliance with the policies described in the study policies document, with the ethical principles that have their origin in the Declaration of Helsinki, with the protocol described herein, and with the standards of Good Clinical Practice (GCP).
292 293 294	The protocol is considered a significant risk device study since the study infusion set is experimental. Therefore, an investigational device exemption (IDE) from the U.S. Food and Drug Administration (FDA) is required to conduct the study.

295	Chapter 2: Study Enrollment and Screening
296	2.1 Subject Recruitment and Enrollment
297 298 299 300 301	Enrollment will proceed with the goal of 240 subjects (120 each on insulins lispro and aspart) completing the main study phase involving use of the study infusion set. A maximum of 300 individuals may be consented for screening to achieve this goal. Subjects who complete at least six wear periods will be considered as completers. Subjects who have signed consent and started the screening process may be permitted to continue into the trial, if eligible, even if the goal of 240 completers has been reached.
302 303 304 305 306	Study subjects will be recruited from up to 20 clinical centers in the United States. All eligible subjects will be included without regard to gender, race, or ethnicity. Each site may contribute a maximum of 25 subjects toward the target of 240 who complete the main study phase. If the enrollment of one insulin type reaches its enrollment goal, that insulin cohort may be closed and only subjects using the insulin in the other insulin cohort would then be eligible for study enrollment.
307	2.1.1 Informed Consent and Authorization Procedures

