308 309 310 311	Potential eligibility may be assessed as part of a routine-care examination or via interaction with the potential subject following a direct inquiry (e.g., resulting from IRB-approved recruiting materials) or a referral from another source. Before completing any procedures or collecting any data that are not part of usual care, electronic informed consent will be obtained.
312 313 314 315 316 317 318	The potential study subject will be provided with the Informed Consent Form to read and will be given the opportunity to ask questions either in-person, via phone/videoconference, or by mail or email. If the potential subject is interested in the study, the investigator will schedule a virtual or in-person visit to discuss the study, and if the potential subject agrees to participate, that individual will electronically sign the Informed Consent Form through the JCHR study website, and the enrolling investigator will also electronically sign the document. A copy of the electronically signed consent form can be printed by the subject and another copy will be printed by the site to add to the subject's study record.
319 320 321 322 323	As part of the informed consent process, the subject will be asked to sign an authorization for release of personal information. This may be done electronically with the consent, or on paper if the site requires their own process. The investigator, or his or her designee, will review the study-specific information that will be collected and to whom that information will be disclosed. After speaking with the subject, questions will be answered about the details regarding authorization.
324 325 326	A subject is considered enrolled when the informed consent form has been electronically signed by all parties and HIPAA authorization has been provided. No study procedures may be performed before the completion of the informed consent documentation.
327	2.2 Subject Inclusion Criteria
328	Individuals must meet the following inclusion criteria to be eligible to participate in the study.
329	1. Age 18 to 80 years old inclusive
330	2. Generally, in good health, as determined by the investigator
331	3. Living in the United States with no plans to move outside the United States during the study
332	4. Diagnosis of T1D for at least 12 months
333 334	5. Minimum of 6 months of insulin pump experience and at least 3 months of current experience with a Tandem pump

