1071 1072 1073 1074 1075	above distribition will be	and in hyperglycemia in days 1-3 versus after day 3 will be assessed with the CGM metrics % time 180 mg/dL, % time above 250 mg/dL, and mean glucose. Summary statistics appropriate to their ations, boxplots will be used to compare data in days 1-3 versus after day 3. Formal comparisons done using paired t-tests (or non-parametric analogs if the data are not approximately normally ated) to account for the correlated data from the same subject.	

1076	8.8 Safety Analyses	
1077 1078 1079	All enrolled subjects will be included in these analyses and all their safety events up to the end of study will be listed. In particular, any AEs involving hyperglycemia/ketosis will include an assessment whether or not it corresponded to an infusion set failure.	
1080	The circumstances of all reportable adverse events as defined in the protocol above will be summarized.	
1081	8.9 Baseline Descriptive Statistics	
1082 1083 1084	Baseline demographic and clinical characteristics of the cohort of all enrolled subjects with at least one wear will be summarized in a table using summary statistics appropriate to the distribution of each variable. Will include:	
1085	■ Age	
1086	■ Gender	
1087	 Race/ethnicity 	
1088	 Diabetes duration 	
1089	■ HbA1c	
1090	■ BMI	
1091	 CGM metrics (including estimated HbA1c) 	
1092	 Insulin type 	
1093	■ Infusion set type	
1094	8.10 Planned Interim Analyses	
1095	No formal interim efficacy analyses are planned for this study.	
1096	8.11 Multiple Comparison/Multiplicity	
1097 1098	Since this is an exploratory and a single arm trial, there will be no formal adjustment for multiple comparisons.	

1099	Chapter 9: Data Collection and Monitoring
1100	9.1 Case Report Forms and Other Data Collection
1101 1102 1103 1104 1105 1106 1107	The main study data are collected on electronic case report forms (eCRFs). When data are directly collected in electronic case report forms, this will be considered the source data. For any data points for which the eCRF is not considered source (e.g., lab results that are transcribed from a printed report into the eCRF), the original source documentation must be maintained in the subject's study chart or medical record. This source must be readily verifiable against the values entered into eCRF. Even where all study data are directly entered into the eCRFs at office visits, evidence of interaction with a live subject must be recorded (e.g., office note, visit record, etc.).

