	5.8.3	Insulin Metrics by Day of Infusion Set Wear	9
6	Desc	ription of Statistical Methods	10
	6.1	Analysis Cohorts	10
	6.2	Analysis of the Primary Endpoint	10
	6.3	Analysis of the Secondary Endpoints	10
	6.3.1	SteadiSet IIS Success Rate	10
	6.3.2	CGM Endpoints	10
	6.3.3	Insulin Endpoints	11
	6.3.4	Pump Endpoints	11
	6.3.5	Tolerability Endpoints	11
	6.4	Analysis of the Exploratory HbA1c Endpoint	12
	6.5	Usability, Satisfaction & Preference Survey	12
7	Safet	y Analyses	12
8	Inter	vention Adherence and Retention Analyses	12
9	Base	line Descriptive Statistics	13
10	Plani	ned Interim Analyses	13
11	Subg	roup Analyses	14
12	Mult	iple Comparisons	14
13	Addi	tional Tabulations and Analyses	15
14	Refe	rences	15

1 Study Overview

- 2 This document outlines the statistical analyses to be performed for the SteadiSet Insulin Infusion
- 3 Set study.

1

- 4 This is an unblinded, single arm, prospective, multicenter study to assess the efficacy and safety
- 5 of the SteadiSet insulin infusion set (IIS) while using a Tandem pump with t:slim X2 Control-IQ
- 6 in adults with type 1 diabetes (T1D). Enrollment will proceed with a goal of 240 participants
- 7 completing the trial, ~120 who will use HumalogTM (insulin lispro) and ~120 who will use
- 8 NovoLogTM (insulin aspart). Participants will be recruited from up to 20 clinical sites, each
- 9 contributing a maximum of 25 participants. All participants will use the SteadiSet IIS with the
- study pump for 12 wear periods of up to 7 days each. The efficacy analysis will include
- participants who complete at least 1 wear period. The safety analysis will include all enrolled
- 12 participants.

13 **2** Consistency

- 14 This SAP does not conflict with the study protocol statistics chapter (version indicated on the
- 15 title page). Additional analyses and tabulations have been included in this Statistical Analysis
- 16 Plan that are not included in the protocol.

17 **3 Statistical Hypotheses**

- 18 The primary outcome is percent of successfully inserted SteadiSet IIS that are not withdrawn
- from use prior to 7 days (168 hours) due to the reasons listed in section 5.2.
- 20 The null/alternative hypotheses are:
- Null Hypothesis: The success rate is 75%.
 - Alternative Hypothesis: The success rate is different from 75% (two-sided).

23 4 Sample Size

22

31

- 24 The study is projected to enroll up to 300 participants such that 240 complete the trial: ~120 who

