- wears of the investigational infusion set will be included; all data from a personal pump (if used
- during the study) will not be counted. Any dropouts will be counted as zero use for the remainder
- of the study.

168 **5.8.1 Overall**

- Overall insulin metrics will be calculated over the entire follow-up period. A minimum of 21
- 170 complete days are required to calculate total daily insulin metrics. Baseline insulin delivery will
- be obtained from the Demographics CRF, which describes the week prior to the Screening visit.

172 5.8.2 Insulin Metrics by Study Week

- 173 Insulin metrics will be calculated for each week of the study. A minimum of 6 complete days of
- insulin data is required to calculate insulin metrics for a week.

175 5.8.3 Insulin Metrics by Day of Infusion Set Wear

- 176 Insulin metrics will also be tabulated by day of infusion set wear over the entire study. A day is
- each subsequent 24-hour period since the current set is inserted. Participants must provide a
- minimum of six complete days of insulin data to be included in the calculation for insulin metrics
- on that day.

180 **6 Description of Statistical Methods**

181 **6.1 Analysis Cohorts**

- Analysis of the Primary Efficacy endpoint will include participants who successfully insert at
- least one investigational infusion set.
- 184 The analysis of the Key Secondary endpoint and the safety endpoints will include all participants
- who attempt to insert at least one investigational infusion set.
- Analyses of all other endpoints will include participants who successfully insert at least one
- investigational infusion set. Intention-to-treat is not relevant since this is not a randomized trial.

188 **6.2** Analysis of the Primary Endpoint

- The proportions of successfully inserted investigational infusion sets that last at least 7 days will
- be tabulated overall and by infusion set location. Reasons reported for removal (main and
- secondary) will be tabulated. All tabulations will be done separately for each insulin type
- 192 (Humalog and Novolog).
- Analysis will be done separately for each insulin type. Kaplan-Meier estimates will be reported
- along with a curve used to estimate the proportion of infusion sets that last at least 7 days.
- 195 Successfully inserted infusion sets that are removed prior to day 7 without meeting the stated
- 196 failure criteria in section 5.2 (Primary Efficacy Endpoint) will be treated as censored

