- 257 Summary statistics appropriate to the distributions will be tabulated for baseline and follow-up
- 258 HbA1c values. A paired t-test will compare the central lab HbA1c values measured at the final
- study visit versus the Day 0 value, and a two-sided 95% CI will be given for the mean difference.
- 260 Participants will be included in the analysis only if they have a central lab value at both times. If
- 261 the paired differences appear skewed, a signed rank test will be used instead. Boxplots will be
- drawn at baseline and follow-up, and scatter plots will be drawn for baseline versus follow-up.
- 263 If analyses are performed separately by insulin type, results over the follow-up period will be
- 264 categorized according to the insulin type in use at baseline.

265 6.5 Usability, Satisfaction & Preference Survey

- Survey responses will be tabulated for each of the three visits, and appropriate summary statistics
- will be reported.
- The following comparisons will be made between survey results: the 2-Week visit versus
- baseline, the Final visit versus baseline, and the Final visit versus the 2-Week visit. The System
- Usability Scale portion of the questionnaire will be scored according to published guidelines¹
- and compared between surveys as a single unit. Other questions will be converted to a 0–100
- scale and corresponding questions will be compared between surveys individually. Differences
- will be analyzed with paired t-tests or signed rank tests, as appropriate. Ninety-five percent
- 274 confidence intervals will be derived from these tests.
- 275 If these analyses are performed separately by insulin type, results over the follow-up periods will
- be categorized according to the insulin type in use at baseline.

7 Safety Analyses

- All enrolled participants will be included in the safety analyses and all their adverse events up to
- the end of the study will be listed.
- Adverse events will be tabulated overall and by wear period, which will be from the time of
- insertion until the time of the next insertion. Adverse events reported after the final wear period
- will be assigned to the final wear period. Whether or not the adverse event occurred while the
- study infusion set was being used will be indicated as will the relationship of adverse events to
- 284 the study device. Any AE involving hyperglycemia/ketosis will include an assessment of

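### The SAP and protocol give two safety populations and two safety windows, so the DKA and severe-hypoglycemia rates can include people and time never exposed to the device

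*SAP*

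**What the plan says.** **Population.** SAP 6.1: "The analysis of the Key Secondary endpoint and the safety endpoints will include all participants" who attempt at least one insertion. SAP 1: "The safety analysis will include all enrolled" participants. SAP 7: "All enrolled participants will be included in the safety analyses and all their adverse events up to" the end of the study are listed. Protocol 8.8 agrees with SAP 7: "All enrolled subjects will be included in these analyses and all their safety events up to the end of study". Protocol 2.1.1 fixes what enrolled means: "A subject is considered enrolled when the informed consent form has been electronically signed by all parties" and HIPAA authorization has been given. Screen failures are therefore enrolled.

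**Window.** SAP 5.4 runs "from the day of enrollment through the day of the final study visit or the day of" "the first insertion + 98 days", taking the earlier date. Protocol 1.3.2 and 8.4.3 define the same endpoints from the day of insertion to the day of removal in each wear period. Protocol Chapter 8 is not uniform, since 8.5 item 4 brings in all reported adverse events and 8.8 goes to the end of the study.

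**Rates.** SAP 5.4 lists severe hypoglycemia and DKA per 100 person-years. Neither document defines the person-time.

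**Consistency.** SAP 2 states that the SAP does not conflict with the protocol's statistics chapter, which contains 8.4.3, 8.5 and 8.8.

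**The concern.** Two analysts working faithfully from these documents could report different denominators for the proportion of participants with an adverse event, and different DKA and severe-hypoglycemia rates. One would follow SAP 6.1 and protocol 8.4.3. The other would follow SAP 1, SAP 7 and SAP 5.4, which puts never-exposed people and pre-device days into figures meant to describe the device.

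Protocol 1.2 says the study is to support a regulatory submission, and protocol 1.5.1.3 names hyperglycemia and ketosis as consequences of set failure. The DKA rate should therefore be reproducible and refer to exposed time. If the choice is left open, it will be made after the data are seen.

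**Working it through.** The documents state no safety figure (person-years, expected rate or safety N), so there is none to reproduce. The check compares the rules and then illustrates their size.

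**1. Rules side by side**

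| Source | Who | From | To |
|---|---|---|---|
| SAP 6.1 | insertion attempters | – | – |
| SAP 1 | all enrolled | – | – |
| SAP 5.4 | – | enrollment | earlier of final visit and first insertion + 98 days |
| SAP 7 (listing) | all enrolled | – | end of study |
| Protocol 1.3.2, 8.4.3 | – | each insertion | each removal |
| Protocol 8.5 item 4, 8.8 | all enrolled; all reported events | – | end of study |

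One consented person who never attempts an insertion is enough to make SAP 6.1 incompatible with SAP 1, SAP 7 and protocol 8.8. An event between consent and first insertion, or on a day with no set in place, counts under SAP 5.4 but not under protocol 8.4.3.

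**2. Population effect.** Protocol 2.1 says "A maximum of 300 individuals may be consented for screening to achieve this goal", the goal being 240 completers. If the goal is met and all 300 are consented, attempters number between 240 and 300. The ratio of incidences is 240/300 = 0.80 at the extreme, so the all-enrolled denominator lowers an incidence by 0% to 20%. With 10 affected participants: 10/240 = 4.2% and 10/300 = 3.3%.

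**3. Pre-device time.** Protocol 2.4 allows 30 days from enrollment to completion of screening. Protocol 3.1 allows 14 more to the initiation visit, where the first set is inserted. The outer limit is 30 + 14 = 44 days. The schedule of visits places consent at the screening visit, and protocol 3.1 lets the two visits coincide, so the lag can also be 14 days or less, down to zero.

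**4. Rates for one event in 240 participants.** Person-years = 240 × days / 365.25, and rate = 100 / person-years. Exact Poisson limits for one event are 0.0253 and 5.572. Full follow-up is assumed.

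| Days per participant | Person-years | Rate per 100 PY | 95% CI |
|---|---|---|---|
| 84 (12 × 7 wear days) | 55.20 | 1.81 | 0.05 to 10.1 |
| 98 (no lag, to cap) | 64.39 | 1.55 | 0.04 to 8.7 |
| 112 (14 + 98) | 73.59 | 1.36 | 0.03 to 7.6 |
| 142 (44 + 98) | 93.31 | 1.07 | 0.03 to 6.0 |

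The widest contrast between the protocol 8.4.3 reading and the SAP 5.4 reading is 142/84 = 1.7-fold.

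**5. The 98-day cap (minor).** Nominal latest final visit: 12 × 7 + 7 = day 91, so the cap does not bind. At the 192-hour limit in protocol 1.4: 12 × 192/24 = 96 days, + 7 = day 103, which is 103 − 98 = 5 days past the cap. Gaps between wears, or replaced early failures (protocol 3.1.2), could move it later. The cap has no meaning for someone who never inserts.

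**The case against.** Several points on the other side stand.

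- *The wider window has support in the protocol.* Protocol 8.5 item 4 and 8.8 take all reported events to the end of the study, so part of the tension lies within the protocol. SAP 5.4 still differs from 8.4.3, and SAP 6.1 still differs from 8.8.
- *The cap has a basis.* The protocol summary gives a subject duration of up to 14 weeks, and 14 × 7 = 98. Reaching day 103 without gaps or replacements needs every set worn to the limit and the full visit window used.
- *Person-time can be inferred.* The rates sit under the SAP 5.4 window, so that window is the natural denominator. Protocol 7.6 uses data up to withdrawal, and 3.5.3 asks early discontinuers for a final visit. Loss to follow-up is left open: SAP 5.7.2 substitutes the last contact for CGM, but nothing equivalent is given for safety. The natural reading is also the one that includes the pre-device days.
- *SAP 2 cites a protocol version on a title page not available here.* The conclusion assumes v5.0 or a version with the same text. Protocol 1.3.2 is outside the statistics chapter, so only 8.4.3 and 8.8 count against SAP 2.

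A reader might infer that events after day 98, or before the first insertion, disappear from the report. The documents do not support that. SAP 7 lists all adverse events to the end of the study, tabulates them overall and assigns those reported after the last wear to the final wear period. Late events fall outside only the SAP 5.4 counts and rates; pre-insertion events are missing only from the by-wear split. Nor is the end-of-study span a third endpoint window: it is a rule for listing.

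**Conclusion.** The inconsistency is real and should be resolved before analysis. The population rule conflicts within the SAP and with protocol 8.8, and the endpoint window conflicts with protocol 8.4.3. The SAP 2 statement is incorrect on both counts, subject to the version assumption above.

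The size is moderate at most: up to a 20% relative reduction in a participant-level incidence, and up to a 1.7-fold difference in a rate (1.81 against 1.07 per 100 person-years for one event). These are outer limits. They assume the recruitment goal is met, full follow-up, the longest permitted lag before insertion, and an event that falls in both windows. An event before insertion would count only in the wider window and could reverse the direction. Confidence intervals for so few events are far wider than the difference.

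A reader might infer that the device's safety conclusion or the primary result is undermined. Neither follows: safety is descriptive and the primary endpoint does not use these definitions.

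**What to change.** In the SAP:

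1. **One safety set** for incidences and rates: participants who attempt at least one insertion, as SAP 6.1 already says. Amend SAP 1 and SAP 7 to match. List separately any adverse events in consented people who never attempt an insertion, and events before the first insertion.
2. **One window** in SAP 5.4: first insertion attempt to the final visit, or to last contact or withdrawal if that visit is missed. Take the numerator and person-time of both rates over that window.
3. **The cap**, if kept, applies to both numerator and person-time, with later events listed.
4. **On-device count:** report the protocol 8.4.3 count using the flag SAP 7 already plans for events during set use.
5. **SAP 2:** replace the no-conflict statement with a list of the differences from protocol 8.4.3 and 8.8. Align the protocol wording at its next amendment.

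No new data are needed. The costs are edits in several SAP sections, IRB review of any protocol change, and moving non-inserters from the main tables to a listing. Adopting all enrolled throughout would take fewer edits, but it would keep unexposed people in the denominators.
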